## Study protocol

The protocol of the 2 randomised groups, is briefly summarized:

**HF-cardiologist group (control):** Usual care provided at a HF Unit was planned. A HF-cardiologist was responsible for prescription and titration, also based on European Society of Cardiology guidelines and addenda and control nurse for clinical evaluation and self-care education, similar to the HF-nurse group with the exception of the titration process. The number of visits depended on each hospital's organization.

CONTROL GROUP PROTOCOL: Usual Care in the HF Units or Programmes (The characteristics of the usual care will be assessed using questionnaires)
CARDIOLOGIST: prescription and drug dosing decisions
HF NURSE: clinical assessment, patient and family education and ensuring patients receive appropriate care in the event of decompensation
General practitioner or internal medicine specialist: in centres where such doctors are part of the team, they may perform follow-up or manage decompensation

**HF-nurse group (intervention):** The protocol was based on the European Heart Failure (HF) Guidelines. HF-nurse requirements were 400-hour HF training and at least 2 years of experience. HF-nurses worked in a team with a HF-cardiologist. Initial drug prescription and expected rate of titration was made by the cardiologist, while the titration process planning was made by HF-nurse. Weekly or biweekly face to face visits were planned, and biweekly drug up-titration, alternating different drugs, was considered. Clinical and analytical evaluation and patient education prior to each increase were required. Dose adjustment of just one drug at each visit, safety checklist review and routine supervision by cardiologist were established. The titration process was tailored to each individual. Cardiologist availability for consultation or visit and early care for decompensation were also established. (See Tables)


(1) Review patient discharge report and case history (patient interview and health record).
 
(2) Review initial checklist: Review ACEIs/ARBs, BBs, MRAs: Indications, contraindications, special precautions, allergies.
 
    Check the records for ACEIs/ARBs, BBs, MRAs: Name, initial and target dose, dose titration schedule: dose and increase time. Alternate titration of drugs.
 
    Review drug interactions: Hypotensive drugs, bradycardia-inducing drugs and other drugs that may interact with renal function or K levels.
 
(2b) Review checklist for dose increases: review standard problems and solutions, consult/refer, increase dose if appropriate
 
(3) Conduct clinical assessment and record findings: signs and symptoms, BP, HR, weight, volume status.
 
    (3b) Assess: Coughing if on ACEIs. Gynecomastia if on spironolactone
 
(4) Record lab test results: Cr and GFR, K. (4b) Assess results: Cr, GFR, K, Na (4c) Issue lab test request form: Cr, GFR, K, Na.
 
    (4d) Request complete blood tests at 12 weeks
 
(5) Perform ECG (5b) Perform extra ECG if HR < 50 bpm.
 
(6) Provide education: understanding signs and symptoms of HF and their monitoring, causes, flexible recommendations on diuretics and when and how to seek advice/ medical attention, diet...
 
    (7) Assess and discuss self-care: Measurements of BP, HR, and weight; self-care booklet; taking all medications correctly. (7b) Self-care scale
 
(8) Provide/explain: appointment schedule, list of drugs
 
(9) Underline possibility of contact over the phone or face-to-face in the event of worsening, to ensure early care
								

HF: heart failure; BB: beta blockers; ACEI: angiotensin converting enzyme inhibitor; ARB: angiotensin II receptor blockers; MRA: mineralocorticoid receptor antagonists. BP: Blood Pressure. HR: Heart Rate. AV block: Atrioventricular block. GF: Glomerular Filtration. K: Potassium. Na: Sodium. ECG: Electrocardiogram
								

CHECKLIST FOR STARTING TITRATION: ACEIs/ARBs (adapted from 2012 ESC guidelines  )		
HF nurse review Indications, contraindications and precautions checked by the nurse as an extra level of safety, similar to the monitoring of allergies		Cardiologist: (A) Agree / (D) Disagree-concern. Measure proposed, Solution yes/no
Name and Surname(s) /patient number:	Date:	
Are ACEIs indicated? NYHA II-IV and LVEF ≤ 40%.	Yes/No	
Are ACEIs contraindicated? Angioedema, bilateral renal artery stenosis, severe aortic stenosis, risk of pregnancy/pregnancy	Yes to some/ No to all	
ACEIs precautions/specialist advice needed? Plasma creatinine (Cr) >2.5 mg/dl, GFR <30 ml/min/1.73 m  .		
Serum potassium (K) > 5 mmol/l (mEq/l), asymptomatic severe hypotension (SBP < 90 mmHg)	Yes to some /No to all	
Prescription, dosing, rate of titration and observations noted in patient health record?	Yes/No	
Baseline BP, creatinine and K levels noted in patient health record	Yes/No	
Dose increases and monitoring planned? (*)	Yes/No	
Education provided to patient and family?	Yes/No	
Patient understanding of drug regimen and adherence checked?	Yes/No	

Checklist for FOLLOW-UP VISITS: INCREASES IN ACEIs/ARBs (adapted from 2012 ESC guidelines  )			
HF nurse (*) Number of increases: 1 st , 2 nd Dose increase		Cardiologist (**): 1 st /2 nd increase: Agree A /Disagree-concern D, measure proposed. Solution? yes/no	
Name and Surname(s) /patient number:	Date:		
Laboratory tests completed? Cr, GFR, K, Na	Yes/No		
Worsening of renal function? Yes /No			
Cr > 30% of baseline : yes/no      Cr > 50% of baseline: yes /no      Cr > 3 mg, GFR < 25 ml/min/1.73 m  : Yes/No	Yes/No		
	Recorded and doctor notified? Yes /No		
Standard solution tried? Review nephrotoxic medication, K supplements or K-sparing agents			
Reduce diuretics if no signs of congestion      Reduce ACEI/ARB dose by half,			
Seek specialist advice, request further tests	Yes / No; Which?		
Increase in creatinine? > 100% Yes/No      3.5 mg Yes/No      GFR < 20 ml/min/1.73 m  : Yes/No			
Discontinue ACEIs/ARBs      Seek urgent advice from the specialist			
K => 5,5 Recorded and doctor notified?      Yes /No			
Standard solution tried? Same as for worsening of renal function yes/no.      low potassium diet Yes / No; Which?			
K => 6			
Standard solution tried? Same as before, seek urgent specialist advice, ECG, discontinue medication      Yes /No; Which?			
Clinical assessment made of volume status? Euvolaemic? Yes/No			
If hyper-hypovolaemic, possible causes reviewed? ↓ Diuretic dose/diet adjusted?      Other factors? Yes/No; measure used:			
Symptomatic low BP? Yes/No			
Standard solution tried? : Consider other hypotensive drugs, reduce/ discontinue nitrates, Ca-antagonists...			
Decrease the dose of diuretics, if no signs of congestion,      Manage timing of hypotensive drugs, seek advice      Yes/No; which?			
New-onset cough (without expectation or fluid overload)?      Yes /No      Recorded and doctor notified? Yes /No			
Patient educated/understands: a) desired effects yes/no, b) adverse effects yes/no, c) avoiding NSAIDs not prescribed by a physician and salt substitutes high in K      yes/no, d) when and how to seek advice/medical attention Yes/No			
Medication adherence checked? Yes /No      Education reinforced and measures taken to support adherence if appropriate? Yes/No			
New dose? Yes /no. Dose increased? Yes /No, if no, reason: Maximum dose increase made: doubling of the previous dose? Yes /No			
Time since previous dose increase ≥ 2 weeks?      Yes /No Dose reduction: Yes /No; Reason			
(*) The HF nurse completes the checklist prior to every dose increase			
(**) The HF cardiologist reviews the checklists (completed by the nurse) of all patients under titration every other week			
NYHA: New York Heart Association. LVEF: left ventricular ejection fraction. Cr Creatinine. GF Glomerular Filtration. K: Potassium. SBP: systolic blood pressure. ECG: Electrocardiogram.			

CHECKLIST FOR STARTING TITRATION: BBs (adapted from 2012 ESC guidelines  )		

HF nurse review Indications, contraindications and precautions checked by the nurse as an extra level of safety, similar to the monitoring of allergies
 
Name and Surname(s) /patient number: _____ Date: _____
 
Are BBs indicated? NYHA II-IV and LVEF ≤ 40%. Yes/No
 
Are BBs contraindicated? Asthma, 2nd or 3rd-degree AV block (in the absence of permanent pacemaker) Yes to some/ No to all
 
BBs precautions/specialist advice needed? NYHA IV, recent/current HF exacerbation, persistent signs of congestion - try euvolaemia, AV block, HR <60 bpm, hypotension < 90 mmHg. Other bradycardia-inducing drugs: verapamil, diltiazem (discontinue), digoxin, amiodarone, ivabradine Yes to some /No to all
 
Prescription, dosing, rate of titration and observations noted in patient health record? Yes/No
 
Baseline BP, HR, no 2nd or 3rd-degree AV block, no asthma noted in patient health record Yes/No
 
Dose increases and monitoring planned? (*) Yes/No
 
Education provided to patient and family? Yes/No
 
Patient understanding of drug regimen and adherence checked? Yes/No
		
Cardiologist: (A) Agree / (D) Disagree-concern. Measure proposed, Solution yes/no
 
A
 
A
 
A
 
A
 
A
 
A
 
A
 
A

Checklist for FOLLOW-UP VISITS: INCREASES IN BBs (adapted from 2012 ESC guidelines  )		

HF nurse (*) Number of increases: 1st, 2nd Dose increase
 
Name and Surname(s) /patient number: _____ Date: _____
 
BP, HR, if HR <50 bpm, ECG, changes in weight/ fluid status: performed/assessed? Yes /No
 
HR < 50 bpm? Yes /No IF HR < 50 bpm, AV block, sinus node dysfunction? Yes /No Recorded and doctor notified? Yes /No
 
Standard solution tried? Review other bradycardia-inducing drugs, digoxin, amiodarone, ivabradine If HR < 50 bpm and worsening of symptoms, reduce the BB dose by half Yes / No; Which?
 
Clinical assessment made of volume status? Euvolaemic? Yes/No
 
If hyper-hypovolaemic, possible causes reviewed? ↓ Diuretic dose/diet adjusted? Other factors?
 
If hypervolaemia is not resolved with other measures (diuretics, others), reduce BB dose by half Yes/No; measure used:
 
Symptomatic low BP? Yes/No Standard solution tried? : Consider other hypotensive drugs, reduce/ discontinue nitrates, Ca-antagonists... Decrease the dose of diuretics, if no signs of congestion, Manage timing of hypotensive drugs, seek advice Yes/No; which?
 
Patient educated/understands: a) desired effects yes/no., b) adverse effects yes/no, c) when and how to seek advice/medical attention Yes/No
 
Medication adherence checked? Yes /No Education reinforced and measures taken to support adherence if appropriate? Yes/No
 
New dose? Yes/No. Dose increased? Yes /No, if no, reason: Maximum dose increase made: doubling of the previous dose? Yes /No
 
Time since previous dose increase ≥ 2 weeks? Yes /No Dose reduction: Yes /No; Reason
		
Cardiologist (**): 1st/2nd increase: Agree A /Disagree-concern D, measure proposed. Solution? yes/no

(*) The HF nurse completes the checklist prior to every dose increase
 
(**) The HF cardiologist reviews the checklists (completed by the nurse) of all patients under titration every other week
		

NYHA: New York Heart Association. LVEF: left ventricular ejection fraction. Cr Creatinine. GF Glomerular Filtration. K: Potassium. SBP: systolic blood pressure. ECG: Electrocardiogram.
		

CHECKLIST FOR STARTING TITRATION: MRAs (adapted from 2012 ESC guidelines  )		Cardiologist: (A) Agree /
HF nurse review Indications, contraindications and precautions checked by the nurse as an extra level of safety, similar to the monitoring of allergies		(D) Disagree-concern. Measure proposed, Solution yes/no
Name and Surname(s) /patient number:	Date:	
Are MRAs indicated? NYHA II-IV and LVEF≤ 35% despite ACEIs/ARBs and BBs, ischaemic heart disease.	Yes/No	A
Are MRAs contraindicated? Eplerenone-strong CYP3A4 inhibitors, e.g., ketoconazole, itraconazole, nefazodone, telithromycin, clarithromycin, ritonavir, or nelfinavir,	Yes to some/ No to all	A
MRA precautions /specialist advice needed? Plasma creatinine (Cr) >2.5 mg/dl, GFR< 30 ml/min/1.73 m2. Serum potassium (K) > 5 mmol/l (mEq/l)	Yes to some /No to all	A
Pharmacological interactions reviewed: K supplements, K-sparing diuretics (amiloride, triamterene, and combinations with furosemide) nonsteroidal anti-inflammatory drugs, trimethoprim/trimethoprim-sulfamethoxazole, salt substitutes high in K	Yes /No	A
Prescription, dosing, rate of titration and observations noted in patient health record?	Yes/No	
Baseline creatinine and K levels noted in patient health record	Yes/No	
Dose increases and monitoring planned? (*)	Yes/No	
Education provided to patient and family?	Yes/No	
Patient understanding of drug regimen and adherence checked?	Yes/No	

Ocultar el par

Checklist for FOLLOW-UP VISITS: INCREASES IN MRAs (adapted from 2012 ESC guidelines  )		Cardiologist (**): 1 st /2 nd increase:
HF nurse (*) Number of increases: 1 st , 2 nd Dose increase		Agree A /Disagree-concern D, measure proposed. Solution? yes/no
Name and Surname(s) /patient number:	Date:	
Laboratory tests completed? Cr, GFR, K, Na Performed ≥after 1-4-8-12 weeks after start/ dose increase	Yes/No	
Worsening of renal function? Yes /No		
Creatinine>2.5 mg, yes/no	GFR<30 ml/min/1.73 m  : yes /no	Recorded and doctor notified? Yes /No
Standard solution tried? Review nephrotoxic medication, K supplements or K-sparing agents		
Reduce diuretics if hypovolaemic	Reduce MRA dose by half,	
Seek specialist advice, request further tests		Yes / No; Which?
Elevated creatinine? 3.5 mg Yes /No	GFR < 20 ml/min/1.73 m^2: Yes/No	
Discontinue MRA	Seek urgent advice from the specialist	
K => 5,5 Yes /No	Recorded and doctor notified?	Yes /No
Standard solution tried? Same as for worsening of renal function yes/no.	low potassium diet yes /no	Yes / No; Which?
K=>6		
Standard solution tried? Same as before, seek urgent specialist advice, ECG, discontinue medication		Yes /No; measure used:
Clinical assessment made of volume status? Euvolaemic? Yes/No		
If hyper-hypovolaemic, possible causes reviewed? Yes/No	Diuretic dose/diet adjusted?	Other factors? Yes/No; Which?
Gynecomastia if on spironolactone: doctor notified? Yes/No		
Patient educated/understands: a) desired effects yes/no., b) adverse effects yes/no, c) avoiding NSAIDs not prescribed by a physician and salt substitutes high in K yes/no d) when and how to seek advice/medical attention yes/no		
Medication adherence checked? Yes /No	Education reinforced and measures taken to support adherence if appropriate? Yes/No	
New dose? Yes /no. Dose increased? Yes /No, if no, reason:		
Time since previous dose increase ≥ 4 weeks? Yes /No	Dose reduction: Yes /No; Reason	
(*) The HF nurse completes the checklist prior to every dose increase		
(**) The HF cardiologist reviews the checklists (completed by the nurse) of all patients under titration every other week		
NYHA: New York Heart Association. LVEF: left ventricular ejection fraction. Cr Creatinine. GF Glomerular Filtration. K: Potassium. SBP: systolic blood pressure. ECG: Electrocardiogram.

Study identification

Official Title: Safety and Effectiveness of Drug up Titration by Nurses Specialized in Heart Failure (HF) Patients.

ClinicalTrials.gov Identifier: NCT02546856.

Document Date: March 1, 2015

Statistical Analysis

The analysis was performed on an intention-to-treat basis. Both the Student's t-test (or the non-parametric Wilcoxon test if continuous data are not normally distributed) and the chi-squared test (or Fisher's exact test) were used to compare the baseline socio-demographic and clinical characteristics of patients in the two groups. The effect attributable to the intervention was estimated by comparing the differences in the relative dose of BB (primary end-point of the study), ACEI, ARB and MRA reached between the groups, assessed at 4 months after starting titration, and the 95% confidence interval was calculated.

All variables with a p value <0.20 were included as explanatory variables in a multivariate model, with relative dose as the response variable. The effect of time was estimated in two repeated measurements for each subject, using mixed linear regression models with fixed effects (time, intervention, interaction between time and intervention) and random effects (specific effect of each subject and centre at the reference level and the effect of time). These models took into account the longitudinal structure of the two repeated measurements, as well as the hierarchical and multicentric structure of the data. All the statistical analyses were performed, using SAS System v 9.4, with statistical significance set at p<0.05.

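### Covariates for the adjusted relative-dose model are chosen by p<0.20 in the trial's own data, from an unidentified test, with no baseline covariate kept regardless (minor)

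*SAP*

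**What the plan says.** The second paragraph of the SAP's Statistical Analysis section sets the rule: "All variables with a p value <0.20 were included as explanatory variables in a multivariate model, with relative dose as the response variable". It gives no candidate list, no screening test and no covariate that is always included.

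The only tests described variable by variable are in the first paragraph. They are the t or Wilcoxon tests and the chi-squared or Fisher tests, which "were used to compare the baseline socio-demographic and clinical characteristics of patients in the two groups". The SAP does not link them to the 0.20 threshold.

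The intervention effect is described separately, also in the first paragraph, as "comparing the differences in the relative dose of BB (primary end-point of the study), ACEI, ARB and MRA reached between the groups". The time point is 4 months, and the estimate carries a 95% CI. No covariates are mentioned there.

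The mixed models follow directly after the screening rule: "The effect of time was estimated in two repeated measurements for each subject, using mixed linear regression models". Their fixed effects are time, intervention and the interaction of the two. Centre is already covered among the "random effects (specific effect of each subject and centre at the reference level and the effect of time"). The SAP does not say whether the multivariate model and the mixed model are the same, or when the two measurements are taken. The Protocol has no statistical text that settles these questions.

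**The concern.** The Protocol describes two randomised groups, so any baseline difference between them is due to chance. A screen on those differences selects covariates by accident of allocation and not by how well they predict dose. Strong predictors are usually left out, the contents of the adjusted model cannot be known in advance, and its standard errors do not match the true variability of the estimate.

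A screen on association with relative dose does keep strong predictors, but it uses outcome data to build the model. The SAP's sentence allows either procedure, and they behave differently. What is at stake is the precision and predictability of the adjusted estimate.

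**Working it through.** **Inputs.** From the SAP: screening threshold 0.20 and significance level 0.05 (taken as two-sided; the SAP does not say). The documents give no sample size, SD, effect size, correlation or number of candidates, so there is no figure of the plan's own to reproduce. Assumed: 100 patients per arm, equal allocation, one baseline covariate with correlation r = 0.3, 0.5 or 0.7 to the outcome, and an effect of 0.398 SD (80% power unadjusted).

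**Reading A: the p values are the between-arm baseline tests.**

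1. *Entry.* Under randomisation P(p<0.20) = 0.20 for each covariate. With two independent prognostic factors, both enter in 0.2² = 4% of trials and neither in 0.8² = 64%.

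2. *Reported CI width.* Let s = √(1−r²) be the residual SD after adjustment, so s = 0.954, 0.866, 0.714. The mean width relative to fixed adjustment is about (0.8 + 0.2s)/s = 1.04, 1.12, 1.32.

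3. *True SD of the estimate.* The screen adjusts exactly when the imbalance z is large, with cut-off c = 1.2816. The share of imbalance variance removed is E[z²; |z|>c] = 2[cφ(c) + 0.10] = 2[1.2816 × 0.1755 + 0.10] = 0.65. The SD relative to fixed adjustment is therefore √[(1−0.65r²)/(1−r²)]:
   - r = 0.3: √(0.9415/0.91) = 1.017
   - r = 0.5: √(0.8375/0.75) = 1.057
   - r = 0.7: √(0.6815/0.51) = 1.156

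   Simulated SDs agree (unadjusted/screened/fixed: 0.141/0.137/0.135, 0.142/0.130/0.123, 0.142/0.117/0.101). About 65% of the available variance reduction is kept.

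4. *Type I error and power*, by simulation with 40,000 replicates per cell. The screened analysis is ANCOVA if the baseline t-test gives p<0.20, and a t-test otherwise.

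| | r = 0.3 | r = 0.5 | r = 0.7 |
|---|---|---|---|
| Type I error, screened | 4.4% | 3.8% | 2.5% |
| Power, screened | 81.0% | 83.3% | 86.6% |
| Power, fixed adjustment | 83.4% | 89.8% | 97.5% |
| Power lost (points) | 2.4 | 6.5 | 10.9 |

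   Results at 50 and 150 per arm are almost the same. Repeat runs at r = 0.5 put the type I error between 3.6% and 4.0%.

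5. *Many candidates.* With an assumed total of 160 patients, 20 candidates and one real predictor (r = 0.5), the SDs are 0.158 unadjusted, 0.152 screened and 0.139 fixed. The share of variance reduction kept is (0.158² − 0.152²)/(0.158² − 0.139²) = 0.00186/0.00564, about one third. Type I error is 4.0%.

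**Reading B: the p values are for association with relative dose.** With one candidate, type I error is 4.9 to 5.1% and power matches fixed adjustment to 0.1 point. A predictor with r = 0.3 is missed in 3.5 to 5% of trials at 50 per arm, and in at most 0.2% at 100 or more.

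**If the multivariate and mixed models are one.** A time-constant covariate entered as a main effect cancels from the within-patient change, so with complete data the time-by-intervention estimate does not move. In 20 simulated data sets the change was below 1e-13. The screen would then matter only for the intervention main effect, or when data are missing.

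**The case against.** The strongest defence has four parts.

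- **Reading B is about as plausible as reading A.** The rule opens a new paragraph, does not refer back to the baseline tests, and speaks of explanatory variables for a stated response. On that reading almost nothing is lost. This stands, and it is why the figures for reading A are conditional.
- **The loss of accuracy is smaller than it looks.** A reader might infer from 20% entry, or from the CI widths, that only a fifth of the benefit of adjustment survives. That holds only for mean reported CI width. The screen acts when imbalance is worst, so with one covariate about 65% of the variance reduction is kept. This also stands, though the share falls when many irrelevant candidates are screened.
- **The comparison tied to the primary endpoint does not use the screen.** A reader might infer that the primary beta-blocker result is compromised. The SAP describes that difference without covariates, so its text does not support this. It does leave unsaid which analysis decides if the adjusted and unadjusted results differ.
- **Some adjustment may already be present.** Centre is in the mixed models, and baseline dose may be one of the two repeated measurements. The SAP does not say, so neither the presence of that adjustment nor a large omitted correlation can be assumed.

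None of this tells the analyst which test drives the rule or which covariates will be in the model.

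**Conclusion.** The concern holds as a minor one, confined to the adjusted model. The rule leaves that model's covariates unknown in advance. If the screen is on baseline imbalance, the analysis is conservative and loses about 2, 6 to 7 or 11 points of power at r = 0.3, 0.5 or 0.7. Its intervals are also wider than the true variability warrants. If the screen is on association with outcome, the practical cost is close to nil.

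A reader might suspect that data-driven selection inflates false positives. The calculations show no material inflation on either reading.

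Sample size, allocation ratio, correlation and number of candidates are all assumptions. The r = 0.7 figures in particular have no anchor in the documents.

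**What to change.** Delete the p<0.20 rule. Before any outcome comparison by arm, fix a short set of baseline prognostic covariates recorded in both arms. Include them whatever their p values, and keep centre as in the mixed model.

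If relative dose of the same drug class is recorded at baseline, use it either as a covariate or as the first repeated response, not both. Its availability needs checking: for the nurse group the Protocol says "Initial drug prescription and expected rate of titration was made by the cardiologist", which does not show that every patient had a dose of each class before randomisation.

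State that the 4-month beta-blocker difference is primary and the adjusted model supportive, and say whether the multivariate and mixed models are one.

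The cost is a change of SAP wording, a few degrees of freedom, and a check that the chosen covariates exist in both arms.
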